1. LIST OF ABBREVIATIONS AND ACRONYMS

Abbreviations and Acronyms	Description
AE	Adverse Event
ADE	Adverse Device Effect
AIS	American Spinal Cord Injury Association Impairment Scale
ASIA	American Spinal Cord Injury Association
BMI	Body Mass Index
BDI-II	Beck Depression Inventory II
CDE	Common Data Elements
CDISC	Clinical Data Interchange Standards Consortium
CDMS	Clinical Data Management System
CI	Confidence Interval
CFB	Change From Baseline
DPC	DP Clinical Inc.
DSMB	Data and Safety Monitoring Board
eCRF	Electronic Case Report Form
FDA	Food and Drug Administration
GCP	Good Clinical Practice
HDE	Humanitarian Device Exemption
ICH	International Conference on Harmonisation
IDE	Investigational Device Exemption
ISNCSCI	The International Standards for Neurological Classification of Spinal Cord Injury
ITT	Intent-To-Treat
LEMS	Lower Extremity Motor Score
MedDRA	Medical Dictionary for Regulatory Activities
MRI	Magnetic resonance imaging
NINDS	National Institute of Neurological Disorders and Stroke
NLI	Neurological Level of Injury
ODS	Output Delivery System

Abbreviations and Acronyms	Description
QC	Quality Control
QLI-SCI III	Ferrans and Powers Quality of Life Index - Spinal Cord Injury III
PCFB	Percent Change From Baseline
PLGA-PLL	Poly((lactic-co-glycolic acid)-co-poly-(L-lysine))
PT	Preferred Term
RTF	Rich Text Format
SAE	Serious Adverse Event
SADE	Serious Adverse Device Effect
SAP	Statistical Analysis Plan
SAS	Statistical Analysis System
SCI	Spinal Cord Injury
SCIM	Spinal Cord Independence Measure
SD	Standard Deviation
SOC	System Organ Class
SOP	Standard Operating Procedure
SSEP	Somatosensory Evoked Potential
TESE	Treatment Emergent Safety Event
UADE	Unanticipated adverse device effect
TLFs	Tables, Listings and Figures
WHODrug	World Health Organization Drug Dictionary
ZPP	Zone of Partial Preservation

2. INTRODUCTION

This Statistical Analysis Plan (SAP) is prepared to provide a more technical and detailed elaboration of the principal statistical features stated in the protocol. The SAP will ensure that the tables, listings, and figures that will be produced and statistical methods that will be used are complete and accurate and will allow valid conclusions to be drawn. In the development of this SAP, the following documents were used:

- Protocol InVivo-100-101 (version 12.1), June 29 2017
- Electronic Case Report Form (eCRF), October 7 2017

The principles in the following guidance documents are followed in preparation of this SAP:

- International Conference on Harmonisation (ICH) E3 (1995): Structure and Content of Clinical Study Reports [1]
- ICH E6 (1996): Guideline for Good Clinical Practice [2]
- ICH E9 (1998): Statistical Principles for Clinical Trials [3]

In the event that a discrepancy is found between the descriptions in the statistical section of the protocol and this document, the description in this document supersedes the descriptions in the statistical section of the protocol.

3. STUDY OVERVIEW

InVivo Therapeutics Corporation has developed an investigational *Neuro-Spinal Scaffold*TM or “Scaffold” for the treatment of Spinal Cord Injury (SCI) to address this unmet medical need.

A prospective, open label, multicenter, non-randomized, single arm pivotal study of this investigational product is being conducted to assess its overall safety and probable benefit. Participation will be limited to subjects suffering from complete AIS A functional spinal cord injury T2 – T12 presentation. The Scaffold is intended for use only in subjects presenting with recent (≤ 7 days since injury) spinal cord injuries that do not involve penetrating injury to the cord or complete severing of the cord. With the exception of Scaffold implantation, subjects are treated according to standard of care at a qualified trauma center, have comprehensive post-injury rehabilitation, and are followed on-study for a period of 10 years from Scaffold implantation.

3.1 Study Objectives

3.1.1 Primary Objectives

To evaluate whether the Scaffold is safe and demonstrates probable benefit for the treatment of complete T2-T12 spinal cord injury.

3.1.2 Regulatory Objective

This is a Humanitarian Device Exemption (HDE) Probable Benefit study to demonstrate safety and probable benefit in support of future studies and an HDE application with subsequent approval.

3.2 Study Design

This is an HDE probable benefit, open-label, non-randomized, single-arm, multicenter study to evaluate the safety and probable benefit of the poly(lactic-co-glycolic acid)-b-poly(L-lysine) Scaffold (“Scaffold”) in subjects with thoracic AIS A traumatic spinal cord injury at neurological level of injury of T2–T12.

The study will be conducted at up to 40 sites in the U.S, Canada and the European Union by qualified Investigators who have been trained on the surgical Scaffold implant procedure in order to obtain 16 subjects (overriding the 20 subjects planned in the protocol) in the Primary Endpoint Analysis Set, defined as all subjects with a successful Scaffold implant, no major

protocol deviations that affect data quality (Section 6.1.2), and a complete 6-month Primary Endpoint Follow-up Visit. After receiving the Scaffold and following discharge, subjects will participate in a comprehensive rehabilitation program (Section 7.3 of protocol). For the first 24-months after implantation of the Scaffold, Follow-up and Long-term Follow-up assessments will be conducted at either the study site or the rehabilitation center depending on the preference of the Investigator and subject, and provided appropriate Institutional Review Board (IRB)/Research Ethics Committee (REC)/Research Ethics Board (REB) approvals are in place. The Long-term Follow-up annual visits for years 3 through 10 will be conducted over the telephone.

A schedule of assessments can be found in Section 3.2.2.

The European Multicenter Study about Spinal Cord Injury (EMSCI) database was used to set the benchmark for the Objective Performance Criterion (OPC) in this HDE Probable Benefit study. This large database of almost 2,600 subjects is being updated continuously. A recent paper including almost 400 subjects with thoracic (T2–T12) complete (AIS A) SCI (same population evaluated in this study) [4] carefully delineated the ISNCSCI-based neurologic outcomes over 48 weeks for subjects segmented by three thoracic level groupings (T2–T5, T6–T9, T10–T12) as well as outcomes for the entire thoracic group. This paper clearly demonstrates that outcomes are poorer for higher level injuries. The subjects in this HDE Probable Benefit study will have similar demographics and mechanisms of injury as in the EMSCI database.

Although standard of care in rehabilitation has changed significantly over the past several decades with introduction of new experimental devices such as exoskeletons, nothing has been demonstrated to improve neurologic outcome in patients with thoracic complete SCI. As evidence of the lack of effect of rehabilitation modernization with respect to AIS category changes, the results are similar for the U.S. Model Systems, EMSCI, and Sygen databases. Published data from the EMSCI, U.S. Model Systems, and Sygen databases found approximately 13%–16% of subjects (thoracic AIS A) spontaneously improved AIS grade by one or more level at six or more months post-injury [4–6]. The neurologic outcomes published from these databases are very consistent, establishing community norms for spontaneous neurologic recovery after SCI. As level of injury is the one criterion which does appear to influence neurologic outcome, assuming a similar distribution of location of injury as these larger databases, establishing a study success goal or OPC of at least 25% of subjects demonstrating an improved AIS grade by one or more level at the 6-month Primary Endpoint Follow-up Visit post-Scaffold implantation is a rigorous efficacy requirement in this population. Thus, the current study will be deemed a success if at least 25% of subjects demonstrate an improved AIS grade by one or more levels at 6-month Primary Endpoint Follow-up Visit post-Scaffold implantation (the final visit for the Primary Endpoint).

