3.2.1 Sample Size Considerations

The study planned to enroll up to 36 subjects to ensure 20 subjects in the Primary Endpoint Analysis Set (Section 5.1). The sample size was determined for the purpose of the study without a formal statistical null hypothesis.

At the time of Primary Endpoint Analysis, it was determined to close enrollment with 16 subjects meeting the Primary Endpoint Analysis Set criteria.

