4. STUDY ENDPOINTS AND DEFINITIONS

4.1 Primary Efficacy Endpoint

The primary endpoint is the AIS grade at the 6 month follow-up visit. Improvement in AIS grade of one or more levels (i.e. a grade of B, C, D, or E) at the 6 month follow-up visit will be considered a success.

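### The 25% success criterion is called rigorous, yet at the SAP's own 13–16% spontaneous rate 16 subjects meet it about 14–25% of the time with no device effect, and no confidence interval is fixed for the result

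*SAP*

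**What the plan says.** SAP section 3.2 (Study Design) reports that published databases found that "approximately 13%–16% of subjects (thoracic AIS A) spontaneously improved AIS grade by one or more level at six or more months post-injury". From this it derives an objective performance criterion (OPC) of 25%, on the condition that one is "assuming a similar distribution of location of injury as these larger databases", and states that this criterion "post-Scaffold implantation is a rigorous efficacy requirement in this population". The decision rule follows: "the current study will be deemed a success if at least 25% of subjects demonstrate an improved AIS grade".

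Section 6.2.1 (Primary Endpoint Analysis) repeats the rule on the observed proportion and asks for the number and percentage of improvers. It does not ask for an interval. Section 7.4.1 (Statistics Reported) mentions 95% confidence intervals only in general terms, to be given where judged suitable, and does not link them to the primary endpoint.

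On size, section 3.2.1 says "The sample size was determined for the purpose of the study without a formal statistical null hypothesis". The plan had been for 20 subjects in the Primary Endpoint Analysis Set, but "it was determined to close enrollment with 16 subjects meeting the Primary Endpoint Analysis Set criteria". Section 5.2 confirms that no formal test is planned.

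On timing, section 4.1 says "The primary endpoint is the AIS grade at the 6 month follow-up visit". The published rate refers to six months or later, and section 3.2 says of one source that it "carefully delineated the ISNCSCI-based neurologic outcomes over 48 weeks".

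**The concern.** Calling a success criterion rigorous says that it is hard to meet without a real effect. Whether that is so depends on the background rate, the threshold and the number of subjects. The SAP gives all three and never combines them. The gap between 13–16% and 25% looks comfortable as a difference between percentages. With 16 subjects it is the difference between an expected 2.1 to 2.6 improvers (16 × 0.13 and 16 × 0.16) and a required 4.

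At stake is what a pass can be taken to mean. Section 3.1.2 says the study is meant to support a humanitarian device exemption application. Followed as written, the plan can report success against a criterion it describes as rigorous on a result fully compatible with the spontaneous recovery it cites. Nothing in the plan ensures that an interval appears beside the result to show this.

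**Working it through.** The SAP states no alpha, power or sample-size derivation, so there is no figure of its own to reproduce. The check computes how the stated rule behaves.

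**Inputs**

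- Subjects analysed: n = 16, originally 20 (sections 3.2 and 3.2.1).
- Rule: observed proportion at least 25% (sections 3.2 and 6.2.1). 0.25 × 16 = 4, so 4 improvers are needed; 0.25 × 20 = 5, so 5 were needed under the original plan.
- Spontaneous rate p: about 0.13 to 0.16 (section 3.2).

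**Chance of meeting the criterion with no device effect**

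P(X ≥ r) = 1 − Σ C(n, k) p^k (1 − p)^(n−k), summed over k = 0 to r − 1.

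For n = 16 and r = 4:

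- p = 0.13: 1 − (0.1077 + 0.2575 + 0.2886 + 0.2013) = 0.1448 (from unrounded terms).
- p = 0.16: 1 − (0.0614 + 0.1873 + 0.2675 + 0.2378) = 0.2460.

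| True improvement rate | n = 16, at least 4 | n = 20, at least 5 |
|---|---|---|
| 13% | 14.5% | 10.8% |
| 16% | 24.6% | 20.6% |
| 25% | 59.5% | 58.5% |

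Closing at 16 instead of 20 raises the chance of a pass with no effect by 3.7 points at 13% (14.48 − 10.83) and 4.0 points at 16% (24.60 − 20.59).

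**What a pass looks like with its interval**

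Clopper-Pearson two-sided 95% limits for x of n are the 2.5% quantile of Beta(x, n − x + 1) and the 97.5% quantile of Beta(x + 1, n − x).

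| Result | Observed | Exact 95% CI | Position relative to 13–16% |
|---|---|---|---|
| 4/16 | 25.0% | 7.3–52.4% | contains all of it |
| 5/16 | 31.3% | 11.0–58.7% | contains all of it |
| 6/16 | 37.5% | 15.2–64.6% | contains 16%, excludes 13% |
| 7/16 | 43.8% | 19.8–70.1% | wholly above it |
| 5/20 | 25.0% | 8.7–49.1% | contains all of it |

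**Sensitivity to the background rate**

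The SAP does not give the spontaneous rate at the 6-month visit itself or for this study's own injury levels. Taking 10% and 20% as an assumed range, the chance of a pass at n = 16 with no device effect is 6.8% and 40.2%.

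**The case against.** The strongest reply is that the SAP does not claim inference. It describes a probable-benefit study, says there is no null hypothesis and no test, and presents results mainly as tabulations because the sample is small. Rigorous is then a judgement about where the threshold sits, some 1.6 to 1.9 times the background rate (25/16 and 25/13), and section 6.2.1 says plainly that success means meeting this criterion. The count and percentage will be shown, so any reader can work out the interval. Table shells are not in the file and may include one. The background rate is approximate and refers to six months or later, so the 14–25% is conditional.

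Part of this stands. No stated error rate is breached, the absence of a test is disclosed, and the probabilities depend on the rate applying here. Results of 7/16 or better would have an interval wholly above the cited range. An exact interval on the imputed analysis also treats imputed outcomes as observed, although counting most missing outcomes as not improved is ordinary practice.

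The rest does not remove the fault. A binary success rule has a pass probability whether or not a hypothesis is named, and section 3.2 asserts a property of the rule that its own figures do not support. Section 7.4.1 lets an analyst omit the interval and still comply. The All Treated analysis repeats the same rule, and the sensitivity analysis changes only how missing grades are handled. Neither sets the result against spontaneous recovery. Doubt about the background rate makes the rigour of the criterion harder to assert.

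**Conclusion.** The concern holds and should be fixed. With 16 subjects, a device with no effect meets the criterion 14.5% of the time at a 13% spontaneous rate and 24.6% at 16%. A bare pass has an interval that covers the whole cited range.

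These figures rest on two assumptions: that the published rate, reported at six months or later, applies at the 6-month visit, and that the injury-level mix resembles the databases, as section 3.2 itself assumes. The arithmetic is certain. The true background rate for this study is not, hence the 10–20% sensitivity range.

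The fault is one of characterisation and reporting on the primary endpoint. The 25% threshold can stay, but the plan should not call it rigorous or leave the uncertainty around the result to discretion.

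**What to change.** 1. In section 6.2.1 and Tables 14.2.1.1.1, 14.2.1.1.2 and 14.2.1.1.3, require the number, the percentage and the exact (Clopper-Pearson) two-sided 95% CI, with the published spontaneous rate of approximately 13–16% shown for reference. Each table uses its own denominator, stated in its footnote as section 6 already provides.
2. In section 3.2, replace the description of the criterion as rigorous with text such as: With 16 subjects the OPC is met by 4 improvers. If the true 6-month rate equals the published spontaneous rate of approximately 13–16% and the injury-level mix is similar, the chance of meeting it is about 14–25%.
3. Keep the OPC at 25%. In sections 3.2 and 6.2.1, report it as OPC met or not met, and state that meeting it does not by itself show improvement over spontaneous recovery.

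The cost is SAP wording and one more column in three planned tables. No further subjects are needed, and the chance of meeting the OPC is unchanged (59.5% at a true rate of 25%). The drawback for the sponsor is that the criterion is described less favourably and a bare pass is shown as inconclusive against natural recovery.

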3.2.1 Sample Size Considerations

The study planned to enroll up to 36 subjects to ensure 20 subjects in the Primary Endpoint Analysis Set (Section 5.1). The sample size was determined for the purpose of the study without a formal statistical null hypothesis.

At the time of Primary Endpoint Analysis, it was determined to close enrollment with 16 subjects meeting the Primary Endpoint Analysis Set criteria.

3.2.2 Study Assessments Schedules

Study assessments are described in detail in the protocol, and summarized below in Table 1.

Table 1: Summary of Study Procedures

Visit Number	1	2	3	4	5	6	7	8	9	10	11	12	13	14-21	Unscheduled Visit
Visit Name	Screening	Surgery	24-hours Post-implant	48-hours Post-implant	72-hours Post-implant	1-week Post-implant	Hospital Discharge	1-month Follow-up	2-months Follow-up	3-months Follow-up	Primary Endpoint 6-months	12-months Long-term Follow-up	24-months Long-term Follow-up	Annual Telephone Visits ⁶	
Visit Windows		±96 hrs	±6 hrs	±6 hrs	±8 hrs	±1 day	-	±3 days	±4 days	±7 days	±30 days	±30 days	±30 days	±60 days	
Informed Consent	X														
Demographics and Medical/Surgical History	X														
Skeletal Maturity/Bone Age (ages 16–17)							X ⁷								
Complete Physical Examination	X						X				X	X	X		X
Screening Labs ¹	X														
Comprehensive Metabolic Panel ² , Hematology ³	X	X	X	X	X	X	X	X	X	X	X	X	X		X
Erythrocyte Sedimentation Rate, C-Reactive Protein	X						X	X	X	X					X
Vital Signs (for intraop vitals, see Section 7.7.3)	X	X	X	X	X	X	X	X	X	X	X	X	X		X
Vital Capacity for subjects not ventilator dependent	X	X	X	X	X	X	X								
Neuro Exam (include hip abd/add, great toe flex/ext)	X	X ⁴	X ⁴	X ⁴	X ⁴	X	X	X	X	X	X	X	X		X
Pain Assessment							X	X	X	X	X	X			X
ISNCSCI exam	X	X ⁵					X	X	X	X	X	X	X		X
MRI (without contrast)	X				X					X	X	X	X		
SSEP (Section 7.7.10)		X													
Pulmonary function monitoring (Section 7.7.11)		X	X	X	X										
Intraoperative Ultrasounds with photograph		X													
Scaffold Implantation with videography		X													
Bowel, Bladder and Sexual Function Assessments								X	X	X	X	X			X
SCIM III, QLI-SCI III, BDI-II							X	X	X	X	X	X			
Prior & Concomitant Meds/Interventions/Procedures	X	X	X	X	X	X	X	X	X	X	X	X			X
Rehabilitation Therapy Log							X	X	X	X	X	X			
Annual General Health Assessment														X	
End of Study (Year 10 or last study visit only)														X	
Safety Event Monitoring		X	X	X	X	X	X	X	X	X	X	X	X	X	X

1 Screening Labs include a serum Pregnancy Test, Blood Alcohol/Urine Drug Toxicology, Blood Type, and Coagulation Test (PT, PTT, INR).
 2 CMP: BUN, glucose, creatinine, sodium, potassium, chloride, calcium, total protein, albumin, total bilirubin, alkaline phosphatase, aspartate aminotransferase, alanine aminotransferase, carbon dioxide.

3 Hematology: CBC w/Diff, WBC, RBC, platelet count, hemoglobin differential counts.
 4 Following surgery, site will perform neurological exam per standard of care.
 5 Confirmatory ISNCSCI must be within 8 hrs before surgery.
 6 Annual visits for years 3 - 10 are telephone contacts and not clinic visits.
 7 May be performed anytime between screening and Hospital Discharge.

4. STUDY ENDPOINTS AND DEFINITIONS

4.1 Primary Efficacy Endpoint

The primary endpoint is the AIS grade at the 6 month follow-up visit. Improvement in AIS grade of one or more levels (i.e. a grade of B, C, D, or E) at the 6 month follow-up visit will be considered a success.

4.2 Secondary Efficacy Endpoints

Secondary efficacy endpoints include:

1. Changes in neurological level of injury (NLI), sensory scores, motor scores
2. Changes in spinal cord anatomy
3. Changes in bowel function, bladder function and sexual function

4.3 Exploratory Efficacy Endpoints

Exploratory efficacy endpoints include:

1. Changes in bowel function, bladder function, and sexual function
2. Changes in pain
3. Changes in SCIM III overall and Area scores
4. Changes in QLI-SCI III

4.4 Safety Endpoints

Safety endpoints will include the following:

1. General safety assessments
 - Incidence of all safety events (AEs/ADEs) of any kind/seriousness
 - Incidence of all serious safety events (SAEs/SADEs)
 - Incidence of unanticipated ADEs (UADEs)
2. Incidence of the following safety events for assessment of the potential risk associated with the use of Scaffold
 - Scaffold migration or malposition
 - Untoward physiologic reaction to PLGA-PLL materials
 - Scaffold-related loss of motor or sensory neurologic function
 - Increased inflammatory response

- Persistent cerebrospinal fluid leak
 - Damage to adjacent structures post Scaffold implant
 - Re-operation or removal of the Scaffold
 - Hemorrhage into or around the spinal cord causing neurologic deficit or possible need for further surgery
 - Surgical infection
 - Increased anesthesia time

 - Adhesion between the spinal cord and dura
 - Postoperative symptomatic or asymptomatic intraspinal cyst or syrinx
 - Post-Scaffold implant on-ventilator time for subjects with sensory deterioration of 2 or more dermatomes determined by either ISNCSCI pinprick or light touch exam as compared to subjects without sensory deterioration of 2 or more dermatomes.
3. Incidence of the following safety events for assessment of the potential risk associated with neurosurgical procedures
- Soft tissue wound infection or dehiscence
 - Surgical injury to the cord

 - Cerebrospinal fluid (CSF) leakage
 - Progressive neurological deterioration beyond that normally expected
 - Bacterial meningitis
 - Cord abscess
 - Failure to alter the natural course of healing from a spinal cord injury
4. Incidence of the following safety events for assessment of the most common general risks of surgery and spinal surgery:
- Adverse reactions to the anesthetic
 - Post-operative pneumonia
 - Blood clots in the legs or elsewhere (deep vein thrombosis) that may travel to the lungs (pulmonary embolus)
 - Infection at the site of surgery
 - Blood loss during surgery requiring a transfusion

- Injury to the nerves or spinal cord resulting in pain or further paralysis
 - Instrumentation breaking, dislodging, or irritating the surrounding tissues
 - Pain from the surgery itself
5. Findings of clinical laboratory tests, including routine blood chemistry and hematology tests
 6. Findings from vital signs measurements
 7. New onset or worsening of depression by Beck Depression Inventory II (BDI-II)

4.5 Definitions

4.5.1 Study Day and Subject-Years

This is the first in human feasibility study of the Scaffold. Various reference time points will be selected for assessment of changes in safety and exploratory efficacy endpoints in the study. Time will be measured as Study Day defined according to Clinical Data Interchange Standards Consortium (CDISC) standard. That is, the date of the start of open spine surgery is Study Day 1. The date before the surgery is Study Day -1. All measurements taken will be displayed in chronological order of the study day to visualize the profile of changes over time.

Last study day for a subject is the subject's last clinical visit date or the date of last telephone contact, whichever is on a later day. If this date is missing for a subject, the last date found in the clinical database (e.g., clinical lab test date or date of vital sign collection) will be used as the last study date for the subject.

Total days on study are the total number of days a subject has been followed up after had the surgery. Mathematically it can be calculated as follows:

$$\text{Total days on study} = \text{last study date} - \text{date of surgery} + 1$$

